Baseline	Flash frozen liver tissue, each ≥ 3 mm, from up to 40 randomized patients a) 20 with Ishak 3 or 4 and no histological or clinical outcome during the study b) 20 with Ishak 5 or 6 who developed clinical decompensation during the study	Serum 300 uL on all patients Blood samples from same patients as liver samples, collected within 90 days of biopsy	

Aim 2 – We will proceed with aim 2 only if results of aim 1 are positive and after HALT-C ancillary studies committee have reviewed those results. Based on the results of Aim 1, a panel of serum biomarkers that differentiates patients with Ishak 3 or 4 and no histological or clinical outcome and patients with Ishak 5 or 6 who developed clinical outcome will be assembled. Results will be considered positive if this panel offers an accuracy $\geq 70\%$ in differentiating these two groups of patients.

Visit	Liver # patients, mm*	Blood # patients, ml	Other (describe) # pts, amount
Baseline		Serum 300 uL from 4 groups of randomized patients (30-40 patients in each group) a) 30-40 patients baseline Ishak 3 or 4 – no progression to cirrhosis on M48 biopsy b) 30-40 patients baseline Ishak 3 or 4 with progression to cirrhosis on M48 biopsy c) 30-40 patients with baseline Ishak 5 or 6 with no decompensation d) 30-40 patients with baseline Ishak 5 or 6 with decompensation	See below table for visual presentation of the 4 patient groups
Month 24 or mid-point between baseline and Outcome		Serum 300 uL from 4 groups of 30-40 patients listed above – at M24 for groups (a-c) and at the half way point between baseline and outcome for patients in group (d)	
Outcome or Month 48		Serum 300 uL from 4 groups of 30-40 patients listed above – at M48 for groups (a-c) and at the time point closest to meeting outcome for patients in group (d)	

Aim 2	Initial Stage	Disease Progression Up to Month 48
--------------	---------------	------------------------------------

Number of Samples	Amount	Sample Type	Initial Ishak Score	Cirrhosis	Decompensation	HCC
30-40	300 µl	Serum	3 to 4	No	No	No
30-40 (with serial samples if available)	300 µl	Serum	3 to 4	Yes	No	No
30-40	300 µl	Serum	5 to 6		No	No
30-40 (with serial samples if available)	300 µl	Serum	5 to 6		Yes	No

Table 1

List of MRM peptides for liver-specific protines

Gene name	Sequence ID	Number of MRM peptide synthesized	Peptide Sequence
Fumarylacetoacetate hydrolase	NP_000128.1	2	AHEHIFGMVLMNDWSAR LLDMELMAFFVVGNGNR
dihydropyrimidinase	NP_001376	2	IPNGVNGVEDR MFMAYK
glycine N-methyltransferase	NP_061833.1	3	AWLLGLLR VWQLYIGDTR SLGVAEGLDQYADGEAAR
argininosuccinate synthetase 1	NP_446464.1	2	BQGYDVIAYLANIGQK GQVYILGR
4-hydroxyphenylpyruvate dioxygenase	NP_002141.1	3	FLHFHSVTFWVGNAAK GYLLQIFTK TEDIITAIR
argininosuccinate lyase	NP_000039.2	3	WSHWILSHAVLTR FVGAVDPIMEK VAEWAQGTF GIVVGIK
aldolase B, fructose-bisphosphate	NM_000035.2	3	ALNDHHVYLEGTLK DGVDFGK
betaine-homocysteine methyltransferase	NP_001704.2	2	VNEAACDIAR AIARELAPER
homogentisate 1,2-dioxygenase	NP_000178.2	2	LLIYTFGK CFYNSDGDPLIVPQK
beta-carotene 15, 15'-monooxygenase 1	NP_059125.2	2	FAVPLHVDK YVFATGVQWSPITPK
glutamate dehydrogenase 1	NP_005262.1	2	YSTDVSDEVK MVEGFFDR
catalase	NP_001743.1	2	HMNGYGSHTFK FYTEDGNWDLVGNNTPIFFIR
retinol-binding protein 4	NP_006735.2	2	YWGVSFLQK FSGTWAMAK
fibrinogen-like 1	NP_004458.3	3	SDGENFNR FSTWDR AQVRLLETR
fructose-1,6-bisphosphatase 1	NP_000498.2	2	TLVYGGIFLYPANK DFDPAVTEYIQK
methionine adenosyltransferase I, alpha	NP_000420.1	3	FVIGGPQDAGVTGR YLEDFTVYHLQPSGR FVIGGPQDAGLTGR
hydroxyacid oxidase 1	NP_060015.1	2	AIFVTVDTPYLGNR LAMALSGCQNVK
aldehyde dehydrogenase 1A1	NP_000680.2	2	IFINNEWHDSVSGK VAFTGSTVEGK
isocitrate dehydrogenase 1	NP_005887.2	2	TVEEAAHGTVTR LIDDMVAQAMK
proteasome alpha 2 subunit	NP_002778.1	2	YNEDLEDAIHTAILTLK HIGLVYSGMSPDYR
DNA directed RNA polymerase II polypeptide B	NP_000929.1	2	MTIHLIECLQK DCQIAGHAAQFLR
glutamate-ammonia Ligase	NP_002056.2	1	DIVEAHYR
asialoglycoprotein receptor 1	NP_001662	1	LLHVK
Asialoglycoprotein receptor 2	NP_550434	2	WVDGTDYR ADHDALLFHLK
Carbamoyl-phosphate synthetase 1, mitochondrial	NP_001866	1	GNDVLVIECNLR LSIQCYLR
3-hydroxy-3-methylglutaryl-Coenzyme A synthase 2	NP_005509	3	YTVGLGQTR VSFEFTEIMNQR SHTGLGR
Transferrin	NP_001054	3	DQYELLCNDTR TAGMNIWGLLYNK TPENFCK
Plasminogen	NP_000292	3	EAQLPVIENK HSIPTETNDR DFHINLFQVLPWLK
complement factor B preproprotein	NP_001701	2	GDSGGPLIVHK IHVYEK
paraoxonase 1	NP_000437	2	HANWTLTPLK IYHSHIDAPK
ceruloplasmin precursor	NP_000087	2	TYCSEPEK SHIAQNSPHTPPR
Interleukin 6 signal transducer	NP_002175	2	HQVPSVQVFSR DFTVLVDR
Peroxisome biogenesis factor 1	NP_000457.1	2	GFLPASLR
Importin 4	NP_078934.3	2	ACYALENFVENLGGPK LLPPLLIQVCK
Purine nucleotide phosphorylase	NP_000261.2	2	FEVGDIMLIR VGFSLITNK ENFSCLTR
Malate dehydrogenase	NP_005908.1	2	LSSAMSAK

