We will proceed with aim 2 only if results of aim 1 are positive. Based on the results of Aim 1, a panel of serum biomarkers that differentiates patients with Ishak 3 or 4 and no histological or clinical outcome and patients with Ishak 5 or 6 who developed clinical outcome will be assembled. Results will be considered positive if this panel offers an accuracy $\geq 70\%$ in differentiating these two groups of patients.

We request serum specimens from a total of approximately 150 patients: 30-40 patients with baseline biopsy showing Ishak 3 or 4 and no progression to histological cirrhosis, clinical decompensation, or HCC; 30-40 patients with baseline biopsy showing Ishak 3 or 4 and progression to histologic cirrhosis but no clinical decompensation or HCC; 30-40 patients with baseline biopsy showing Ishak 5 or 6 and no

progression to clinical decompensation or HCC, and 30-40 with baseline Ishak 5 or 6 and progression to clinical decompensation but not HCC. For those who progressed, we would like to obtain 2 earlier samples at baseline and approximate midpoint to time of cirrhosis or clinical decompensation. It would be desirable to match groups for gender, ethnicity, and HCV genotype.

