Statistical Analysis Plan: As for Aim 1, we will use multiple linear regression with the disease status as a categorical covariate. Adjusted R-Squared, Mallow's Cp, and AIC criteria will be used to ensure reproducibility of the predictive properties of the protein panel in future observations. In order to handle multiple observations made on a subset of study subjects, a random intercept term will be introduced in the linear mixed model. As a secondary analysis, survival analysis methods (proportional and non-proportional hazards regression models) will be used on a subset of subjects with follow-up information on their progression from fibrosis to cirrhosis and/or HCC during the follow-up. There is insufficient information at this point to assess the power and precision of the validation analysis. Therefore, updated sample size assessment will be performed after Aim 1 has been completed, yielding quantitative data on coefficient of variation and on group differences by protein. Tentatively, using the same assumptions as in Aim 1, we expect to have improved sensitivity with 30 patients per group, instead of 20, resulting in an ability to detect a 27% difference in protein levels. We will analyze both individual proteins and all proteins, as well as potentially related, clustered proteins as secondary analyses.

5. Methods & Data Usage

a) Novel technology platforms: Next generation deep sequencing for transcripts (such as Solexa); N-glycopeptide proteomics and multiple reaction monitoring for proteins by mass spectrometry.

b) Protein biomarker panel: See Table 1 for proteins and MRM peptides to be assayed.

c) Assays of liver and serum specimens: We will use multiple reaction monitoring of the 2 or 3 specific peptides associated with each of the 36 proteins in the Table below in an Orbitrap or LTQ-FT mass spectrometer; the peptides have already been designed (Table 1).

d) Statistical design and analysis: See specific sections under Aim 1 and Aim 2.

e) Data usage: We will fully comply with the HALT-C Data Use Agreement. Samples will be labeled with HALT-C subject no. and sample ID. We have no interest in specific-patient identifiers. We will use newly-generated identifiers held by the HALT-C PI to permit longitudinal analyses of serum specimens from the patients studied. We will report all findings on a group basis.

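### In Aim 2 the final group d serum may be drawn after decompensation, and the stated mixed model has no sampling-time term, so effects of the event and drift over time can appear as a group effect

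*Protocol*

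**What the plan says.** The Aim 2 visit table in Part III sets three serum times.

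- **Baseline:** the same for all four groups.
- **Middle sample:** "at M24 for groups (a-c) and at the half way point between baseline and outcome for patients in group (d".
- **Last sample:** month 48 in groups a to c, and "at the time point closest to meeting outcome for patients in group (d".

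Group c is "30-40 patients with baseline Ishak 5 or 6 with no decompensation" and group d is "30-40 patients with baseline Ishak 5 or 6 with decompensation". They share the same baseline stage, so their contrast concerns decompensation.

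Section 4.2 asks, in patients who progressed, for "2 earlier samples at baseline and approximate midpoint to time of cirrhosis or clinical decompensation". Its analysis paragraph regresses protein level on disease status as a categorical covariate. For repeated samples it says that "a random intercept term will be introduced in the linear mixed model". It names no term for sampling time or for time relative to the event, and no rule for sera drawn at or after the event. Matching is wished for on gender, ethnicity and genotype, not on follow-up time. Aim 2 and section 6 state that the markers are meant to predict progression as well as to distinguish groups.

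**The concern.** A sample chosen as nearest to the outcome can lie on either side of it. If it follows decompensation, the protein level may reflect the event or its management rather than anything that came before. Such a sample can support a statement about recognising decompensated disease. It cannot support a statement about predicting it.

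Timing adds a second problem. The small Aim 2 summary table counts progression up to month 48, so group d outcomes fall by then. Their middle sera therefore fall at or before month 24, and their final sera generally before month 48. Any change with time on study that is unrelated to outcome then differs between groups c and d. With no time term, the model assigns that difference to disease status.

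The specimen rule matters most, because it is fixed in this document and decides which stored aliquots are used. No later modelling turns a post-event serum into a pre-event one.

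**Working it through.** The Protocol states no figure for this point, so there is none to reproduce. The check sets the passages side by side and then illustrates the size.

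**Side by side (visit table, Part III)**

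| Sample | Groups a to c | Group d |
|---|---|---|
| First | baseline | baseline |
| Middle | month 24 | half way to outcome |
| Last | month 48 | nearest to outcome, before or after |

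Only the baseline row is comparable in time across groups. The section 4.2 model is not limited to that row, since it is written to take repeated observations.

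**Illustration 1: effect of the event**

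Inputs from the Protocol: CV 0.5 (section 4.1 assumes below 0.5, so this is the upper limit), 30 to 40 per group, three visits. Assumed: a protein with no difference before the event, 40% higher after it; half of the final group d sera drawn after it; intraclass correlation ρ from 0.3 to 0.7; two-sided 5% test.

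1. Mean shift in the final group d sample: 0.5 × 0.40 = 0.20.
2. With three visits per patient, the group effect in a random-intercept model is the difference in patient means: 0.20 / 3 = 0.067.
3. Standard error: SE = 0.5 × √[(ρ + (1 − ρ)/3) × 2/n]. For n = 30 and ρ = 0.5: 0.5 × √(0.667 × 0.0667) = 0.105.
4. False rejection: Φ(δ/SE − 1.96) + Φ(−δ/SE − 1.96). Here δ/SE = 0.067/0.105 = 0.63, which gives 0.097.

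| n per group | ρ = 0.3 | ρ = 0.5 | ρ = 0.7 |
|---|---|---|---|
| 30 | 10.9% | 9.7% | 8.9% |
| 40 | 12.9% | 11.3% | 10.2% |

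This is about 9% to 13% against a nominal 5%. If the shift is varied from 20% to 40% and the affected share from 25% to 100%, the range is about 5% to 29% with 30 per group and 5% to 37% with 40.

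**Illustration 2: timing alone**

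Assumed: a drift of g per year common to both groups, and a group d outcome at year t. The difference in patient means over three visits is [g(2 − t/2) + g(4 − t)]/3 = g(2 − t/2). For t = 2 this equals g, that is 0.05 or 0.10. With ρ = 0.5, false rejection is then 7.6% and 15.8% with 30 per group, and 8.5% and 19.5% with 40. For t from 1 to 3 and g from 5% to 10%, the full range is about 6% to 38%.

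**Who has serial sera**

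Both illustrations follow the visit table, which requests all three visits in all four groups. Section 4.2 asks for earlier samples only in those who progressed, and the summary table lists serial samples only for the two progressing groups. On that reading no fixed-month group c sera exist, so the timing contrast takes another form. Event-related sera would still enter the model for group d and not for group c.

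**The case against.** Much of the case on the other side is fair.

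- **Baseline sera are clean.** They are taken at the same point in every group, and a prediction analysis limited to them would be free of this problem. That stands, but section 4.2 does not limit the analysis in that way.
- **A serum at the outcome has a proper use.** The Protocol also aims at diagnosis and monitoring, and such a sample serves those aims. That stands too. The defect is that the text does not separate diagnostic from predictive use.
- **Time and treatment terms may be left to a statistical analysis plan.** Their absence alone would not be a finding. It matters here because the specimen schedule builds in a timing difference that the stated model does not address.
- **The survival analysis handles timing.** It is secondary and covers progression from fibrosis to cirrhosis and/or HCC, so it does not repair the contrast on decompensation.

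Three stronger readings are tempting, and the documents do not support them.

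- A reader might infer that section 4.2 and Part III contradict each other on group b's midpoint. Part III defines group b by cirrhosis on the month 48 biopsy, so its outcome time is month 48 and its midpoint is month 24. The two agree.
- A reader might infer a false-positive rate of 31% to 40%. That comes from a single test of c against d at the last visit, under the assumptions of illustration 1. The Protocol specifies no such test.
- A reader might infer that group c sera could simply be drawn at times matched to group d. Nothing in the Protocol shows that such off-schedule aliquots exist.

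**Conclusion.** The point holds as a defect in one specimen rule and in the model that uses the specimen. Followed as written, Part III admits post-decompensation sera in group d, places group d sera at event-driven and generally earlier times, and passes both to a model with no time term. The resulting group effect can mix marker signal with effects of the event and with drift.

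The mechanism follows from the text; the size does not. The 9% to 13% rests on an assumed 40% post-event change in half of the final group d sera, an assumed intraclass correlation of 0.3 to 0.7, and three visits in both groups. The drift figures rest on assumed drift rates and event times. The documents do not support saying that Aim 2 as a whole is invalid, since the baseline comparison is unaffected.

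**What to change.** 1. In the Part III visit table, define the last group d sample as the last stored serum on or before the outcome date. If a post-event serum is kept, use it only for diagnostic comparisons and exclude it from every prediction analysis.
2. In section 4.2, add time since baseline as a fixed effect in the mixed model, with treatment arm if it is supplied for Aim 2. Section 5 lists treatment assignment and outcome dates for the Aim 1 data set only, so request the same fields, with sampling dates, for Aim 2. The time term addresses common drift; it does not replace item 1.
3. Reconcile section 4.2 and the summary table, which give serial sera to progressors only, with the visit table, which gives them to all four groups.

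The cost is wording and a few data fields, with no increase in the aliquots requested. Some group d samples will be one visit earlier than under the present rule. Aim 2 starts only after the Aim 1 results have been reviewed, so the change can be made before specimens are pulled.
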